8.5 Adjustment for Multiplicity

If the primary null hypothesis, H_{01} , is rejected at a 2-sided alpha = 0.05 in favor of CSF-1 in the alternative hypothesis, H_{11} , tested as delineated in the primary efficacy analysis section ([Section 12.1](#)), then the study will be considered a success and the following key secondary hypotheses will be tested in hierarchical order, each at a 2-sided alpha = 0.05, where inference will be made on each null hypothesis only if the prior null hypotheses are rejected in favor of CSF-1.

1. Visit 3 (Day 8), 2 hours following Dose 1 (H_{02})
2. Visit 3 (Day 8), 1 hour following Dose 2 (H_{03})
3. Visit 3 (Day 8), 2 hours following Dose 2 (H_{04})

9. Disposition of Subjects

Subject disposition will be presented in terms of the numbers and percentages of subjects who were randomized, completed the study, and discontinued from the study. A discontinued subject is someone who does not complete the 4 protocol-defined study visits. Subjects who are not discontinued from the study will be considered study completers. Disposition will be summarized by treatment arm for all randomized subjects. The reasons for study discontinuation will also be summarized and include: AE, lost to follow-up, physician decision, protocol violation, study terminated by sponsor, withdrawal by subject, death, and other. A subject listing will be provided which includes the date and reason for study discontinuation.

The number of subjects in each of the analysis sets (FAS, PPS, and SAF) will be displayed by treatment arm, with the number of subjects and percentages calculated using randomized subjects as the denominator. The number and percentage of subjects with any (major, or minor) protocol deviations will be summarized by treatment arm and overall for all randomized subjects. Protocol deviations will be classified as major or minor prior to the closure of the database during a masked review of each protocol deviation. Major deviations will be defined as those deviations that potentially affect the analysis of the primary study endpoint.

A subject listing will be provided which includes the date of the deviation, the deviation code and description, and the classification of whether the deviation was deemed major or minor. In addition, subject listings will include treatment arm and ICF signature date, and exclusions from the PPS. There will also be a listing of screen failures.

10. Demographic and Baseline Characteristics

10.1 Demographics

Subject demographic data collected in this study, age, sex, race, ethnicity, and childbearing potential. Subjects who record more than one race will be grouped into a single category denoted as multi-racial, and subjects who record more than one iris color (study eye) will be classified as heterochromia. Sex, race, ethnicity, childbearing potential, and iris color will be presented using descriptive summary statistics with frequency counts and percentages. Age (years) will be summarized with continuous descriptive statistics. Categorical variables will be summarized with number and percentage.

Demographic variables along with two baseline characteristics, iris color of study eye and manifest refraction spherical equivalent (MRSE), will be summarized for the FAS and PPS by treatment arm and overall in tables. A subject listing that includes all summarized demographic and baseline variables will also be provided.

10.2 Baseline Characteristics

Baseline characteristics are measured to ensure the safety and eligibility of subjects at Visit 1 (Day -14 to -1). Subject level listings will be used to present pre-treatment information from the FAS at the eye level when appropriate. Baseline characteristics will be contained in subject listings only and will include:

- Manifest refraction
- Iris color
- Dark-adapted pupillometry
- Fluorescein staining
- Dilated indirect funduscopy

11. Medical History and Concomitant Medications

11.1 Medical History

Medical history will be coded using Medical Dictionary for Regulatory Activities (MedDRA) Version 23.0. Non-ocular medical history will be summarized using discrete summary statistics and presented by treatment arm at the subject level by System Organ Class (SOC) and Preferred Term (PT) using the SAF. Ocular medical history will be similarly summarized at the subject level. If a subject reports the same PT multiple times within the same SOC, then that PT will only be reported once within that SOC. As with the PT, if a subject reports multiple conditions within the same SOC, then that SOC will only be reported once. All SOC and PTs within an SOC category will be ordered by descending frequency based on all subjects.

Listings of medical history will be generated separately for ocular and non-ocular information.

11.2 Prior and Concomitant Medications

Prior and concomitant medications will be coded using World Health Organization (WHO) Drug Dictionary (WHODrug Global B3 March 2020) and summarized to the therapeutic drug class (Anatomical Therapeutic Chemical [ATC] 4 classification) and preferred name (generic drug name). If the ATC 4 classification is not provided, the next lowest classification that is provided in the coding dictionary will be employed. The preferred name will be defined as the active ingredient; if the active ingredient is not provided or includes more than two ingredients (e.g., multivitamins) then the drug name will be summarized as the preferred name. Any uncoded terms will be summarized under the ATC classification of "Uncoded," but the missing preferred term will be replaced by the verbatim term entered in the eCRF.

Concomitant medications are defined as those medications listed as having been taken (1) prior to initiation of study drug administration and continuing for any period of time following the first administration of study drug or (2) at any time following the first administration of study drug. Prior medications are defined as those medications not concomitant, but taken within 30 days of screening Visit 1 (Day -14 to -1). Prior and concomitant medications will be summarized using the SAF. Medications will be tabulated for each

treatment arm using frequency counts and percentages. Subjects may have more than one medication per ATC text. At each level of subject summarization, a subject will be counted once if reporting one or more medications. Percentages will be based on the number of subjects in each treatment arm. The ATC Classes and preferred names within an ATC Class will be ordered by descending frequency based on all subjects.

Summaries will be generated separately for prior and concomitant medications, with ocular and non-ocular data also summarized separately using the SAF. Subject listings will group prior and concomitant medications together, with ocular and non-ocular information presented separately.

12. Efficacy Analyses

The primary efficacy and key secondary efficacy analyses are described in [Section 12.1](#). Sensitivity analyses on the primary and key secondary efficacy endpoints are described in [Section 12.2](#), and will be performed using the FAS.

12.1 Primary and Key Secondary Efficacy Analysis

The primary efficacy endpoint in this study is the percentage of subjects with a ≥ 3 -line (15-letter) gain, from baseline, in best distance-corrected visual acuity (BDCVA) at 40 cm (Precision Vision chart) and no loss in BDCVA ≥ 5 letters (ETDRS chart) at Visit 3, 1 hour following Dose 1 in the study eye. The key secondary efficacy endpoints are defined the same as the primary efficacy endpoint, except for being measured at 2 hours following Dose 1, 1 hour following Dose 2, and 2 hours following Dose 2, all at Visit 3.

The primary and key secondary efficacy analysis will be conducted in the FAS with missing data handled in the following manners:

1. Discontinuation of study drug and non-optimal compliance will be ignored [treatment policy strategy].
2. Withdrawal due to lack of efficacy or AEs: missing data will be singly imputed as failure [hypothetical strategy].
3. Missing data without withdrawal or withdrawal due to reasons other than lack of efficacy or AEs: missing data will be imputed employing Multiple Imputation (MI) using randomized treatment-based Markov Chain Monte Carlo (MCMC) methods.

No subject data will be excluded from the FAS due to protocol violations/deviations. The multiple imputation of missing values will be completed for the continuous measures (BDCVA at 40 cm and BDCVA at 4 m), then the response variable will be determined therefrom. Imputation of failure due to lack of efficacy or AE will be assigned after multiple imputation is performed.

Variables for treatment group, baseline for BDCVA at 40 cm and baseline for BDCVA at 4 m will also be included in the multiple imputation model. 25 complete imputed datasets will be created.

Example SAS® code for the multiple imputation:

```
PROC MI DATA=DATAIN OUT=MI NIMPUTE=25 SEED=118787 minimum=-0.3 maximum=1;
  MCMC INITIAL=EM;
  VAR TRTPN VA40 VA40BL VA4 VA4BL;
RUN;
```

Where TRTPN = treatment group, coded 1 for CSF-1, else 0

VA40 = value of BDCVA at 40 cm for Visit 3, 1 hour after Dose 1

VA40BL = baseline value of BDCVA at 40 cm

VA4 = value of BDCVA at 4 m for Visit 3, 1 hour after Dose 1

VA4BL = baseline value of BDCVA at 4 m

For each imputed dataset, a logistic regression model with baseline BDCVA at 40 cm as a covariate and treatment as a main effect will be used to obtain the treatment effect estimate, odds ratio, and 95% confidence interval (CI) for odds ratio.

Example SAS® code for the logistic model is shown here:

```
PROC LOGISTIC DATA=MI DESCENDING OUTTEST=PARMS COVOUT;
  BY _IMPUTATION_;
  CLASS TRTP;
  MODEL AVALC = BASE TRTP;
RUN;
```

where

- TRTP is the treatment arm (CSF-1, Vehicle);
- BASE is the baseline of BDCVA (letters) at 40 cm in the study eye;
- AVALC is the indicator for efficacy variable (Y, N).

SAS® PROC MIANALYZE will be used to obtain the overall p-value, odds ratio, and 95% confidence interval (CI) for odds ratio.

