5.3 Withdrawal Criteria

A subject may withdraw consent to participate in the study at any time for any reason. Subjects will be withdrawn from the study if any of the following criteria are met:

- Be a female of childbearing potential who is currently pregnant, nursing, or planning a pregnancy; tests positive to a urine pregnancy test at Visit 4; or refuses to use an adequate method of contraception for the duration of the study;
- Have an active ocular infection (bacterial, viral, or fungal), active ocular inflammation (e.g., moderate to severe blepharitis, allergic conjunctivitis, peripheral ulcerative keratitis, scleritis, uveitis) at Visit 2, Visit 3, or Visit 4 in either eye.
- Subjects may also be withdrawn from the study for the following reasons:
 - Adverse Event (AE)
 - Lost to follow-up
 - Death
 - Subject not adequately following required study procedures
 - Study terminated by the Sponsor
 - Other

Subject withdrawals will be documented on the subjects' source document.

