8.6 Subject Disposition

Completed Subjects

A completed subject is one who has not been discontinued from the study and successfully completes all 4 study visits.

Withdrawn Subjects

A subject may be withdrawn for meeting any of the withdrawal criteria as described in Section [5.3](#).

Discontinued Subjects

A discontinued subject is one who does not complete the protocol-defined study visits. A subject may be discontinued at the discretion of the investigator, sponsor, and/or the Institutional Review

Board (IRB). Notification of early discontinuation from the study and the reason for discontinuation will be made to the sponsor and/or [REDACTED]

Prior to discontinuing a subject, every effort should be made to obtain as much follow-up data as possible, and to retrieve all study materials. AEs will be followed as described in [Section 9](#).

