All reported study data will be recorded on the eCRFs supplied by [REDACTED] using iMedNet™. Only the Principal Investigator and authorized study staff according to the Delegation of Responsibilities log are entitled to make entries in the eCRF. After data are entered into the clinical study database, electronic edit checks, and data review will be performed. All data validation specifications and procedures are detailed in the Data Validation Manual as a separate document. When the database has been declared to be complete and accurate, the database will be locked. Any changes to the database after data have been locked can only be made with the approval of the sponsor and [REDACTED] Inc. in consultation with SDC.

The final analyses outlined in this document will be carried out only after the following have occurred:

- All data management requirements are met according to SDC standard operating procedures, including data entry, performance of edit and validation checks, documentation and resolution of data queries, and database lock with written authorization provided by appropriate SDC and sponsor personnel.

- Protocol deviations have been identified and status defined (major/minor deviations), and completed prior to database lock and study unmasking.
- Analysis populations have been determined, and completed prior to database lock and study unmasking.
- Randomized treatment codes have been unmasked.

7. Analysis Sets

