12.2 Sensitivity Analysis for Primary and Key Secondary Efficacy Endpoints

Sensitivity Analysis for the primary and key secondary efficacy endpoints include:

1. All missing data imputed as failure using the FAS
2. Observed data only using the FAS

[figure not shown]
3. Observed data only using the PPS
4. Missing data will be imputed employing tipping point approach. The analysis will be based on the FAS

[figure not shown]
For #1, #2 and #3 sensitivity analyses, the analysis of primary and key secondary efficacy endpoints will be performed using a logistic regression model with baseline BDCVA at 40 cm as a covariate and treatment as a main effect. The odds ratio, and 95% confidence interval (CI) for odds ratio will be provided. p-values will be presented for the main effect of treatment group using a Wald statistic.

Tipping Point Analysis of Primary and Key Secondary Efficacy Variables

Missing primary and key secondary efficacy endpoint values (i.e., binary response values) will be imputed using tipping point approach. First set all records in CSF-1 with missing value as failures and all records in Vehicle with missing value as successes, that is the worst case. The imputed data will be analyzed using a logistic regression model with baseline BDCVA at 40 cm as a covariate and treatment as a main effect. The p-value, odds ratio, and 95% confidence interval (CI) for odds ratio will be provided. If the p-value is less or equal to 0.05 for the worst case, then stop there. If the p-value is greater than 0.05 for the worst case, then set the missing records as failures or successes in all possible combinations from worse case to the best case until the p-value turns from >0.05 to ≤ 0.05 .

14. Safety Analyses

All safety analyses will be conducted using the SAF. In addition to AEs, BCVA at distance under normal and low-luminance testing conditions, findings from slit-lamp biomicroscopy examination, conjunctival redness grading, study drug drop comfort assessment, dilated indirect fundoscopy, and IOP measurements will be summarized descriptively using quantitative and qualitative summary statistics by treatment arm and subject visit, as appropriate. All such measurements related to safety endpoints will also be presented in a detailed subject listing.

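### Does the failure rule for lack-of-efficacy withdrawals break down because no listed discontinuation reason names lack of efficacy?

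*SAP*

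**What the plan says.** SAP Section 12.1 sets three rules for the primary and key secondary endpoints. Under rule 1, stopping study drug and imperfect compliance are ignored. Rule 2 reads: "Withdrawal due to lack of efficacy or AEs: missing data will be singly imputed as failure [hypothetical strategy". Rule 3 applies multiple imputation to the remainder: "Missing data without withdrawal or withdrawal due to reasons other than lack of efficacy or AEs". Protocol Sections 10.7 and 10.10 say the same.

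The order of operations is stated: "Imputation of failure due to lack of efficacy or AE will be assigned after multiple imputation is performed". Everyone with missing data first receives imputed acuities, and the subjects identified under rule 2 are then overwritten as failures.

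SAP Section 9 (Disposition of Subjects) gives the reasons for discontinuation to be tabulated: "AE, lost to follow-up, physician decision, protocol violation, study terminated by sponsor, withdrawal by subject, death, and other". Protocol Section 5.3 has its own list, introduced by "Subjects may also be withdrawn from the study for the following reasons": adverse event, lost to follow-up, death, not following procedures, termination by the sponsor, and other. Adverse event is on both lists. Lack of efficacy is on neither.

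SAP Section 6 lists what must be complete before final analysis. Protocol deviations must be classified, and "Analysis populations have been determined, and completed prior to database lock and study unmasking". It does not mention classifying withdrawals.

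**The concern.** The reason for withdrawal decides whether a missing primary outcome is a failure or an imputed value. If no recorded category says lack of efficacy, that half of rule 2 has nothing explicit to act on. Because failures are assigned after imputation, an unidentified subject keeps a value drawn from a model containing only treatment, the two baseline acuities and the two Visit 3 acuities. Nothing in that model reflects that the subject left because the drops did not work.

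Timing is the second worry. The only masked pre-lock steps described concern deviations and analysis sets. If someone had to judge from free text which withdrawals were for lack of efficacy, the plan does not say that this happens before treatment codes are released. At stake would be a small bias in the primary estimate and a discretionary decision on primary outcome values.

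Two smaller points arise on the same rule. Its bracketed label calls failure imputation a hypothetical strategy, where many statisticians would say composite. Death is also not mentioned by name in any of the three rules.

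**Working it through.** **Inputs.** SAP Section 5 and Protocol Section 10.5 give response rates of 42.5% (CSF-1) and 17.5% (Vehicle), a Pearson chi-squared test at two-sided 0.05, 140 evaluable per arm with power above 97.5%, about 5% discontinuation and about 150 randomized per arm. The split of dropouts by reason, arm and time is not given, so 0 to 8 per arm (5% of 150 is 7.5) is an assumed range.

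**The plan's own figure.** At 140 per arm, power is 99.7% by the pooled normal approximation and also by exact enumeration. This agrees with the stated lower bound of 97.5%.

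**Size of the error if rule 2 is missed.** Assume that a subject left in multiple imputation has the arm's planning rate as expected response; under rule 2 it is 0. With *k* such subjects in an arm of 150, that arm's rate is overstated by (*k*/150) × rate.

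- One subject: 0.425/150 = 0.28 points in CSF-1; 0.175/150 = 0.12 points in Vehicle.
- One or two per arm: net 0.17 or 0.33 points.
- All dropouts, balanced (7.5 per arm): 0.05 × 0.425 − 0.05 × 0.175 = 2.125 − 0.875 = 1.25 points.
- Half or a quarter of dropouts, balanced: 0.62 or 0.31 points.
- Eight in CSF-1 only: 8/150 × 0.425 = +2.27 points.
- Eight in Vehicle only: 8/150 × 0.175 = −0.93 points.
- The sign reverses when Vehicle has more than 0.425/0.175 = 2.43 times as many such subjects as CSF-1.

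The larger cases are upper limits. The 5% covers all reasons through Day 15, including adverse events, which rule 2 already captures. For the primary and key secondary endpoints, only subjects with missing Day 8 data matter.

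**Effect on the conclusion.** The table gives exact power of the chi-squared test at 150 per arm with rule 2 fully applied (the *k* subjects fixed as failures, the rest responding at the planning rates).

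| Lack-of-efficacy failures (CSF-1 / Vehicle) | Expected difference | Power |
|---|---|---|
| 0 / 0 | 25.0 points | 99.8% |
| 8 / 8 | 23.7 points | 99.7% |
| 8 / 0 | 22.7 points | 99.4% |
| 0 / 8 | 25.9 points | 99.9% |

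**What the planned sensitivity analyses cover.** SAP Section 12.2 includes "All missing data imputed as failure using the FAS". This gives every lack-of-efficacy withdrawal with missing data exactly the value rule 2 would give, whatever reason was recorded. The tipping-point analysis also ignores the reason. Its worst case, with 8 missing per arm, has an expected difference of 0.425 × 142/150 − (0.175 × 142/150 + 8/150) = 18.3 points. Power there is 94.5% with the imputed values held fixed.

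**Can the subjects be identified?** SAP Section 9 states how reasons will be summarized; it does not describe the eCRF, which is not among the documents. *Withdrawal by subject*, *physician decision* and *other* can each hold someone who left because the drops did not work, and a by-subject listing of reasons is planned. Protocol Section 8.6 has early discontinuation notified when it happens: "the reason for discontinuation will be made to the sponsor". Under SAP Section 4.2, subjects, investigators, study staff and the sponsor are masked throughout, and under SAP Section 6 the database is locked before final analysis. The information that drives rule 2 is therefore recorded under the mask and then fixed.

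**Label and death.** Renaming the strategy changes no imputed value, estimate or test. Death is listed separately from adverse event in both documents, so read literally it falls under rule 3 as a reason other than lack of efficacy or AE.

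**The case for a change.** The strongest case for a change is that a prespecified primary rule should be executable from the plan alone. An eCRF text field, if there is one, does not say who reads it, by what standard or when. Sensitivity analyses are supportive and do not define the primary estimate. One sentence and a short masked look at no more than about 15 records would settle it.

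Part of this stands. The visible text has no mapping from recorded reasons to rules 2 and 3, and it does not expressly place that step before unmasking. A sentence saying so would be tidy and harmless.

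The stronger claims do not stand. That the classification would be made with codes known is conjecture, since the reasons are collected and locked while everyone concerned is masked. That no category captures these subjects is too strong, since three categories can. Adding a reason to the SAP table would capture nothing new if data collection were already closed. The arithmetic is also generous to the concern: Protocol Section 10.5 says the planning rates already count missing data as failures, so using them as the expected response under imputation and then subtracting failures mixes two conventions. The effect of that is small at 5% missing.

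**Conclusion.** No change follows. The wording of rule 2 and the lists of reasons do not match, but this is missing detail of a kind that analysts resolve sensibly from the recorded reason. If they failed to do so for every planned dropout, the treatment difference would be overstated by 1.25 points when balanced, with one-sided limits of +2.3 and −0.9 points, against a planned difference of 25. Exact power with the rule fully applied stays at 99.4% or above.

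This rests on the planning response rates, on 5% dropout as an upper limit for data missing at Day 8, and on imputed subjects responding at their arm's rate. Dropout well above plan and concentrated in CSF-1 would enlarge the shift, and the all-missing-as-failure and tipping-point analyses would show it. The strategy label is editorial, and a death already falls under rule 3.

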10.5 Sample Size

A total sample size of 280 subjects (140 subjects per arm) yields >97.5% power to establish superiority of CSF-1 to Vehicle in the percentage of study eyes demonstrating a ≥ 3 -line (15-letter) gain from baseline in BDCVA at 40 cm (Precision Vision chart) and no loss of best distance corrected VA ≥ 5 letters (ETDRS at 4m), 1-hour post each dose on Visit 3 (Day 8) assuming a response rate of 42.5% in CSF-1 and 17.5% in Vehicle using a Pearson chi-squared test with a 2-sided significance level of 0.05.

[REDACTED]

Accounting for approximately a 5% discontinuation rate, approximately 150 subjects per arm (approximately 300 total) will be randomized.

Estimates were obtained from the Phase 2 study (18-150-0006) Intent-to-Treat (ITT) population response for pilocarpine 0.4% vs. diclofenac (control), additionally imputing missing data as failures.

At least approximately 30% of subjects will have light (i.e., blue, green, gray, and hazel) iris, and at least approximately 30% will have a brown iris. The actual percentages will vary based on enrollment.

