10.7 Efficacy Analysis

Primary Efficacy Analyses

The primary efficacy endpoint in this study is the percentage of subjects with a ≥ 3 -line (15-letter) gain, from baseline, in best distance-corrected visual acuity (BDCVA) at 40 cm (Precision Vision chart) and no loss in best distance corrected visual acuity ≥ 5 letters (ETDRS chart) at Visit 3, 1 hour following Dose 1 in the study eye. The primary efficacy analysis will be conducted in the FAS with intercurrent events handled in the following manners:

- 1) Discontinuation of study drug and non-optimal compliance will be ignored [treatment policy strategy].
- 2) Withdrawal due to lack of efficacy or adverse events: missing data will be singly imputed as failure [hypothetical strategy].
- 3) Missing data without withdrawal or withdrawal due to reasons other than lack of efficacy or adverse events: missing data will be imputed employing Multiple Imputation (MI) using randomized treatment-based Markov Chain Monte Carlo (MCMC) methodology [hypothetical strategy].

No subject data will be excluded from the FAS due to protocol violations/deviations. The FAS will be used for the primary efficacy analyses. Note that multiple imputations of missing values will be completed for the continuous measures (BDCVA at 40 cm and best distance corrected VA at 4m), then the response variable will be determined therefrom.

[REDACTED]

Descriptive statistics will be presented by treatment group. Testing of the percentage of subjects with at least a 3-line (15-letter) improvement from baseline in BDCVA at 40 cm without a loss of ≥ 5 letters in best distance corrected VA at 4m will be completed separately for the 1 hour and 2 hour time points using a generalized linear mixed model with a binomial distribution including fixed effects of baseline BDCVA at 40 cm as a covariate, daily dose (Dose 1 and Dose 2), treatment, and the interaction of dose with treatment and random effect of subject to account for the correlation within a subject between daily doses. [REDACTED]

[REDACTED]

The adjusted odds ratios and marginal proportions and difference in proportions along with corresponding two-sided 95% Confidence Intervals (CIs) and p-values will be presented.

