4.2 Masking and Unmasking

An independent, unmasked biostatistician who is not otherwise involved in the trial will generate the complete randomized study drug kit list. The subject, study sponsor, medical investigators, and study staff will be masked during the entire randomization process and throughout the course of the study. When medically necessary, the investigator may need to determine what treatment has been assigned to a particular subject. When possible (i.e., in non-emergent situations), [REDACTED] and/or the study sponsor should be notified before unmasking the IP. In emergency situations, the investigator must notify the sponsor within 24 hours after determining that it is necessary to unmask the treatment assignment. The investigator must also indicate in source documents and in the electronic case report form (eCRF) that the mask was broken and provide the date, time, and reason for breaking the mask.

5. Sample Size and Power Considerations

A total sample size of 280 subjects (140 subjects per arm) yields > 97.5% power to establish superiority of CSF-1 to Vehicle in the percentage of study eyes demonstrating a \geq 3-line (15-letter) gain from baseline in BDCVA at 40 cm (Precision Vision chart) and no loss of BDCVA \geq 5 letters (ETDRS at 4 m), 1-hour post

each dose on Visit 3 (Day 8) assuming a response rate of 42.5% in CSF-1 and 17.5% in Vehicle using a Pearson chi-squared test with a 2-sided significance level of 0.05.

A series of horizontal black bars of varying lengths, likely representing redacted text or data. The bars are arranged vertically and span the width of the page. Some bars are longer, while others are shorter, indicating different lengths of redacted content.

Accounting for approximately a 5% discontinuation rate, approximately 150 subjects per arm (approximately 300 total) will be randomized.

6. Data Preparation

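### Should a Visit 3 response missing because of an adverse event or lack of efficacy count as failure even when the subject did not withdraw?

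*SAP*

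**What the plan says.** SAP section 12.1 sets three rules for the primary and key secondary analyses in the full analysis set.

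- Rule 1: "Discontinuation of study drug and non-optimal compliance will be ignored [treatment policy strategy". A value measured after the subject has stopped the drug is used as observed.
- Rule 2: "Withdrawal due to lack of efficacy or AEs: missing data will be singly imputed as failure [hypothetical strategy".
- Rule 3: "Missing data without withdrawal or withdrawal due to reasons other than lack of efficacy or AEs: missing data will be imputed", here by treatment-based MCMC multiple imputation.

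The imputation model in the example code is "VAR TRTPN VA40 VA40BL VA4 VA4BL": treatment, the two acuities that make up the endpoint, and their baselines. Failures under rule 2 are assigned after the imputation.

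Protocol section 10.7 has the same third rule, "Missing data without withdrawal or withdrawal due to reasons other than lack of efficacy or adverse events: missing data will be imputed", and section 10.10 repeats it. SAP section 12.2 adds four sensitivity analyses for the primary and key secondary endpoints. The first is "All missing data imputed as failure using the FAS". The fourth is a tipping-point analysis that starts from the case least favourable to CSF-1.

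**The concern.** Rule 2 reflects a judgement that a response missing because of an adverse event or lack of efficacy should count against the treatment. Rule 3 does not apply that judgement to a subject who has the same cause but stays enrolled. Such a CSF-1 subject has values drawn from a model fitted mostly to subjects on drug, with no term for adverse events, adherence or reason for missingness. Missing at random is least plausible for exactly this subject.

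Relative to failure scoring, imputation adds a fraction of a responder for each such subject, and more in CSF-1 than in Vehicle. The success criterion and the testing hierarchy rest on section 12.1, so a rule that leans towards the active arm there deserves a check.

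**Working it through.** **Inputs.** SAP section 5 gives planning response rates of 42.5% (CSF-1) and 17.5% (Vehicle), a two-sided 5% Pearson chi-squared test, and 140 evaluable per arm with a stated power above 97.5%. For the randomized number it says "Accounting for approximately a 5% discontinuation rate, approximately 150 subjects per arm". The documents give no count of subjects with a value missing for these causes without withdrawal, so counts below are assumptions.

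**The plan's own figure.** Power with 140 per arm at 42.5% v 17.5% is 99.66%, consistent with the stated bound. At 150 per arm it is 99.80%.

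**Distance between the two ways of scoring.** Imputation gives an affected CSF-1 subject an expected response of about 0.425; failure scoring gives 0. Per subject the CSF-1 rate differs by 0.425/150 = 0.28 points. For 3 subjects it is 0.85 points and for 5 it is 1.42. With k affected in CSF-1 and v in Vehicle, imputation raises the difference by (0.425k − 0.175v)/150. That is positive unless v > (0.425/0.175)k = 2.43k. With k = v = 3 it is 0.75/150 = 0.50 points.

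The planning rates already count missing values as failures ("vs. diclofenac (control), additionally imputing missing data as failures", Protocol section 10.5). If 5% were missing in the planning study (an assumption), the observed rates would be 0.425/0.95 = 44.7% and 0.175/0.95 = 18.4%, and the per-subject figure 0.447/150 = 0.30 points.

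**Distance is not bias.** Let t be the true response probability of an affected CSF-1 subject.

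- Error of imputation: (0.425 − t)/150.
- Error of failure scoring: −t/150.
- Failure scoring is closer only if t < 0.425 − t, that is t < 0.2125.

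| t | Imputation error (points) | Failure-scoring error (points) |
|---|---|---|
| 0.175 (Vehicle-like) | +0.17 | −0.12 |
| 0.2125 | +0.14 | −0.14 |
| 0.30 | +0.08 | −0.20 |
| 0.425 (on-drug) | 0 | −0.28 |

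Between Vehicle-like and on-drug, imputation is closer over (0.425 − 0.2125)/(0.425 − 0.175) = 85% of the interval. Dividing both rates by 0.95 leaves that share unchanged. At the Vehicle-like end the gain from failure scoring is 0.167 − 0.117 = 0.05 points per subject.

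**Effect on the conclusion.** With five CSF-1 subjects scored as failure, the CSF-1 rate is 42.5 − 1.42 = 41.08% and power at 150 per arm is 99.56%, against 99.80%. The allowance for discontinuation from every cause is 0.05 × 150 = 7.5 per arm.

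**Who can be affected.** SAP section 9 and Protocol section 8.6 treat a subject who does not complete the scheduled visits as discontinued, and SAP section 9 records the reason, with adverse event among the options. A subject who misses Visit 3 altogether because of an adverse event therefore has a disposition record with that reason. Protocol section 5.3 requires withdrawal for active ocular infection or inflammation found at Visit 3. What remains is mainly a missed timepoint within an attended visit, where staff instil Dose 1 and the primary measurement follows one hour later. It is hard to see how lack of efficacy would remove that measurement for a subject who attends.

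**The case for a change.** The best case for a change is one of consistency. Rule 2 already counts these causes as failure, and nothing in the documents says why leaving the study should decide the matter. The imputation model cannot see the cause. The sensitivity analyses are only supportive under SAP section 8.2, and none isolates this group. At a smaller true effect the choice matters more: at an assumed 30% v 17.5% with 150 per arm, power is 72.2% under imputation and 62.0% if an assumed 5% of CSF-1 subjects, and none in Vehicle, are scored as failure.

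The asymmetry is real, and so is its usual direction. The rest carries less weight. A 5% share equals the entire allowance for discontinuation, placed in one arm and in a group that has not discontinued. The lower power under failure scoring also does not show that imputation is wrong; that depends on t, as above.

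Rescoring by cause would need a cause for each missing value. The visible text records reasons for study discontinuation only, and lack of efficacy is not on the list in SAP section 9. The masked review described there classifies protocol deviations. A cause-based rule would thus replace a criterion that can be read off the disposition record with a judgement, and would make the primary analysis differ from the protocol.

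One wording point stands. The sentence in section 12.1 on the order of steps mentions failure for lack of efficacy or an adverse event without repeating the withdrawal condition. It describes sequence, and the numbered rules define who is affected. A clarifying phrase would be harmless but is not required.

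**Conclusion.** The concern does not hold. The documents agree with each other, and the rule is a defensible choice on which reasonable statisticians would differ. Failure scoring would move the CSF-1 rate by 0.28 to 0.30 points per affected subject, but that measures the distance between two conventions, not an error in the plan. Imputation is closer to the truth whenever the subject's true response probability exceeds 0.2125, and where it is not, down to a Vehicle-like response, the advantage of failure scoring is at most about 0.05 points per subject. With five affected CSF-1 subjects power changes by about 0.2 percentage points, and the all-missing-as-failure and tipping-point analyses in SAP section 12.2 already bracket the effect.

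This rests on the planning rates of 42.5% and 17.5%, on taking the imputed response as roughly the arm's rate, on a true response between Vehicle-like and on-drug, and on few such subjects. Were the true response well below the Vehicle rate, failure scoring would be nearer, by up to 0.28 points per subject. That case is covered by the first sensitivity analysis.
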